## LIST OF ABBREVIATIONS

ACCORD	Academic and Clinical Central Office for Research & Development - Joint office for The University of Edinburgh and Lothian Health Board
AE	Adverse Event
AR	Adverse Reaction
CI	Chief Investigator
CRF	Case Report Form
CSR	Clinical Study Report
CTA	Clinical Trial Authorisation
CTIMP	Clinical Trial of Investigational Medicinal Product
DMC	Data Monitoring Committee
DSUR	Development Safety Update Report
eCRF	Electronic Case Report Form
ECTU	Edinburgh Clinical Trials Unit
EudraCT	European Clinical Trials Database
GCP	Good Clinical Practice
GMP	Good Manufacturing Practice
HAS	5% Human Albumin Solution
HRQoL	Health Related Quality of Life
IB	Investigator Brochure
ICH	International Conference on Harmonisation
IMP	Investigational Medicinal Product
ISF	Investigator Site File
ISRCTN	International Standard Randomised Controlled Trials Number
MHRA	Medicines and Healthcare products Regulatory Agency
PI	Principal Investigator
NIMP	Non-Investigational Medicinal Product
QA	Quality Assurance
REC	Research Ethics Committee

SAE	Serious Adverse Event
SAR	Serious Adverse Reaction
SDV	Source Data Verification
SPC	Summary of Product Characteristics
SOP	Standard Operating Procedure
SUSAR	Suspected Unexpected Serious Adverse Reaction
TMF	Trial Master File
TMG	Trial Management Group
TSC	Trial Steering Committee

## TRIAL SUMMARY

Trial Title	Feasibility of 5% Human Albumin Solution compared with Balanced Crystalloid, as intravenous fluid resuscitation in adult patients with sepsis, presenting as an emergency to hospital
Study Acronym	ABC Sepsis
Clinical Phase	Phase III
Trial Design	Open label two-arm, multicentre, pragmatic, parallel group randomised trial
Trial Participants	Adult patients with community acquired sepsis recruited from the Emergency Department and Medical and Surgical Assessment Units in ~ 15 UK NHS Hospitals.
Planned Number of Participants	300
Planned Number of Sites	~15
Countries Anticipated to be Involved in Trial	UK
Treatment Duration	6 hours
Follow up Duration	90 days; except first 50 patients (180 days)
Total Planned Trial Duration	24 months
Primary Objective	
This trial aims to investigate:
 
 
the feasibility of being able to recruit adults with community acquired sepsis and a National Early Warning Score (NEWS/NEWS2) of <math>\geq 5</math> in the Emergency Department
 
the comparative effectiveness, by determining 30-day mortality, of intravenous 5% Human Albumin compared with intravenous balanced crystalloid in the early resuscitation phase of management of adults with community acquired sepsis.
 

Primary Endpoint	
 
Recruitment rate from screening logs
 
30 day mortality
 

## Secondary Objectives

1. To assess the mortality rate during index hospitalisation, in-hospital and at 90 days;
2. To assess the ability to deliver the trial including the time to first dose, data completeness and participant withdrawal;
3. To quantify the proportion of patients who receive any other fluid apart, from the one being studied, in the first 6 hours after recruitment;
4. To assess the total volume of intravenous fluid in each arm at 6 hours and 24 hours
5. To assess the level of critical care interventions administered;
6. To investigate the length of hospital stay including critical care (HDU/ICU) admission;
7. To investigate the proportion of patients readmitted to hospital in first 90 days after discharge;
8. Delineate the proportion of patients developing any complications including acute kidney injury, pulmonary oedema and allergy including severe allergic reactions;
9. To assess patient quality of life measures using EQ-5D-5L questionnaire;
10. To assess secondary care costs at 30 days.


Secondary Endpoints
	
 
1. In-hospital mortality and 90-day mortality;
 
2. Time to start of IMP;
 
3. Data completeness;
 
4. Study withdrawal;
 
5. Volume of randomised fluid delivered in each arm in the first 6hrs and 24hrs;
 
6. Proportion of participants needing critical care intervention: Intravenous vasopressors, renal replacement therapy and invasive ventilation;
 
7. Proportion of patients who receive any other fluid apart from intervention or control in first 6 hrs after recruitment;
 
8. Proportion of patients admitted to critical care (HDU/ICU); length of stay in critical care (HDU/ICU);
 
9. Length of hospital stay;
 
10. Proportion of patients readmitted in first 90 days after discharge.
 
11. Proportion of patients developing any of: acute kidney injury (Defined by NICE (https://cks.nice.org.uk/acute-kidney-injury#!scenario)); pulmonary oedema (Radiology diagnosis or requirement for rescue management (new diuretic use); and allergy or anaphylaxis (Requirement for rescue management (antihistamines, adrenaline, intravenous fluids, steroids)).
 
12. Health Related Quality of life (EQ-5D-5L) at 7 and 180 days for the first 50 patients.
 
13. Secondary care costs at 30 days (calculated from readmissions and length of stay at ward level and in critical care (HDU/ICU).
 

IMP(s)
	
5% Human Albumin Solution

IMP Route of Administration
	
Intravenous, peripheral or central

Lay Summary of Trial
	
The aim of this research study is to compare two different fluids (Human Albumin Solution (HAS) and Balanced Crystalloid that are given via a drip to patients with severe infection (sepsis). We plan to see which fluid is better, and to see if they have a role in improving a patient’s recovery time, reducing complications and the length of time they stay in hospital. This study plans to find out if there is evidence that one fluid is better overall to determine the need for a subsequent definitive trial.

## 1. INTRODUCTION

### 1.1 BACKGROUND

This trial will investigate the feasibility of delivering an early intravenous fluid resuscitation trial comparing 5% human albumin solution (HAS), (current recommended second line fluid therapy in septic shock) as first line therapy with a balanced crystalloid (routine care; currently recommended first line therapy in international sepsis guidelines) [1,2] in adults with sepsis. Previous trials and meta-analyses show that HAS has a potential benefit in patients with sepsis.

The trial intervention will be delivered in the critical first hours of hospital treatment. Patients will be enrolled in Emergency departments (ED) and Medical and Surgical Assessment Units (AAU). We aim to recruit in all groups of sepsis patients who require intravenous fluid resuscitation, not the minority whose care is delivered or will ultimately be delivered in critical care. This maximises generalisability and relevance to the NHS and is very different from previous HAS or previous international sepsis resuscitation trials. Most sepsis in UK hospitals is not managed in critical care; critical care patients are estimated to comprise around only 5-10% of all patients with suspected sepsis [3,4]. We propose an efficient trial design to investigate feasibility and potential effect size for the proposed primary effectiveness outcome, 30-day mortality.

causally to long-term outcomes, by reducing subsequent inflammation, immune suppression, and organ dysfunction [9]. Guidelines highlight the importance of early antibiotics and intravenous fluid resuscitation, but the delivery of early fluids is logistically challenging and its direct association with outcomes is uncertain [10]. The proposed primary/secondary clinical outcomes all directly reflect or impact on population health and wellbeing. Our focus is on early sepsis intervention, which has plausibility for modifying short and long-term outcomes. We chose not to study an exclusively ICU population, because, in this population, the intervention is later, selection bias is possible, and disease modification is less plausible. This trial will uniquely include all sepsis presenting to hospitals (>90% of sepsis patients in the NHS are managed in a general ward setting), for whom there is very limited research evidence around the timing and type or volume of intravenous fluid resuscitation. This initial study will establish whether a definitive study comparing 5% HAS with the current standard of balanced crystalloid fluid is feasible in this population and setting. If this study is feasible, it will inform the design and conduct of a larger definitive trial with results that will be generalisable to all patients with community acquired sepsis. The cost of sepsis is high, both during index admission and subsequent 'survivorship' [10]. The excess treatment costs for HAS are likely to be around £110/patient, substantially increasing current fluid costs, but HAS use has already increased 2-3 fold in many hospitals since 2012 consistent with data from outside the UK [6]. The potential economic gains (health/social) from effective early sepsis interventions are substantial and lifelong so our definitive study will include a health economic evaluation which will provide key information to guide HAS use in the NHS. For example, a reduction of 1 patient day in ICU would save around £1500 (equivalent to 12-13 units of HAS).

***The main types of intravenous resuscitation fluid:*** The two classes of commonly used intravenous resuscitation fluids are crystalloids ("normal" saline and balanced crystalloid) and colloids (hydroxyethyl starch and albumin) [6,7]. Current UK and international guidelines recommend balanced crystalloids as the first line choice of intravenous fluid in the resuscitation of adult patients with sepsis [1,2]. Recent international and UK data suggest that the use of non-balanced crystalloid remains widespread especially in emergency care settings [6,7]. Starch based colloids are no longer recommended because they were associated with harm in large sepsis and critical care trials.

***Supporting randomised controlled trials, meta-analyses and current research:*** Three large trials include data directly comparing HAS with crystalloid, one included a heterogeneous critical care population using iso-oncotic 4% albumin [31,32] and two only recruited sepsis populations admitted to critical care with hyper-oncotic solution of 20% albumin [33,34]. The reduction in the risk of death from septic shock with albumin as compared to crystalloid fluid was consistent across all three trials and ranged between 2.3% to 6.4% at 28 and 90 days respectively. In the Saline vs. Albumin Fluid Evaluation (SAFE) trial [31], in a general ICU population, HAS had no overall effect but the sepsis sub-group suggested lower mortality. This subgroup demonstrated a 5.2% mortality difference when adjusted for relevant baseline characteristics (35.5% vs. 30.2%; OR 0.71, 95% CI 0.52–0.97, p = 0.03). [32]. However, this post hoc analysis was at best hypothesis generating. The ALBIOS trial

[33] studied ICU patients with severe sepsis (comparing 20% HAS infusion with crystalloid) and found no overall effect on mortality, but lower mortality with HAS in the sub-group with septic shock (RR 0.87; 95% CI 0.77 to 0.99), equating to an absolute risk reduction of 5.3%; HAS also improved cardiovascular stability although, importantly, the treatment goal in this study was serum albumin concentration, not haemodynamic or end organ perfusion markers. The EARSS study in France, recruited 798 patients with septic shock of less than 6 hours duration, but only in ICUs. These patients were randomised to receive: 100 ml of 20% albumin or 1000 ml of 0.9% saline every 8 hours for 3 days. Almost all patients had severe hypoalbuminemia at study inclusion. There were no significant differences in 28 day mortality rates between the two groups (24.1 vs. 26.3%). This study has never been published in full [34].

Several meta-analyses (MA) analysed these data plus results from a number of smaller trials. A MA of 5,534 patients (5 trials) comparing HAS with crystalloids (3,658 severe sepsis; 2,180 septic shock) found HAS was associated with a non-significant difference in 90-day mortality in severe sepsis (odds ratio (OR) 0.88; 95% CI, 0.76 to 1.01;  $p = 0.08$ ) and significantly reduced mortality in septic shock (OR 0.81; 95% CI, 0.67 to 0.97;  $p = 0.03$ ) [35]. A MA of 3878 patients (7 trials) found a non-significant difference in mortality with HAS (RR 0.93; 95% CI 0.86 to 1.01;  $p=0.07$ ), with possibly greater effects in septic shock (RR 0.91; 0.82 to 1.01;  $p=0.06$ ) [36]. Differences between the MAs are likely to relate to the differences in included trials and methodologies, and small total number of participants.

Importantly, none of these trials compare HAS to balanced crystalloid as the early resuscitation fluid in a pre-ICU setting despite these data being extrapolated in guidelines to precisely this environment. A search of trial registries 12th June 2020) found no ongoing trials addressing this research question. These MA support the need for a trial of HAS in early sepsis, powered for a clinically plausible effect size. In this study we will investigate feasibility of delivering a pragmatic trial during the resuscitation phase of treatment of adults with sepsis and provide pilot data that will inform the size of treatment effect between HAS and balanced crystalloid for the planned primary outcome – 30-day mortality - enabling an accurate sample size to be calculated for a subsequent definitive trial.

## 1.2 RATIONALE FOR STUDY

### ***Rationale for balanced compared with non-balanced crystalloid as comparator:***

There has been increasing concern relating to the potential adverse effects of crystalloids such as 0.9% “normal” saline due to the harmful effects of the high chloride content being associated with hyperchloraemic metabolic acidosis [11] and resultant increased risk of acute kidney injury [12]. More recently, three large pragmatic trials have shown divergent results in relation to the potential harm associated with non-balanced crystalloids. The SPLIT trial showed no difference in the rates of acute kidney injury in ICU patients [13], whereas the SALT-ED in Emergency Department [14] and SMART in ICU patients [15] showed a reduced risk of acute kidney injury and other important clinical outcomes with balanced crystalloids when compared with non-balanced crystalloids. We chose to mandate balanced crystalloid based on these recent large trials, We consider this an important stipulation in this feasibility trial given heterogeneity of use of balanced crystalloid in ED.

***Mechanism of action of Human Albumin Solution:*** It is widely believed that colloids exhibit properties that result in them being superior to crystalloids for expansion of the intravascular space, enhancing cardiac output and thus end organ oxygenation and perfusion. Additionally, due to their larger molecules, they do not leak through the endothelial layer into the interstitium resulting in less tissue oedema than with crystalloids [14-16]. These properties should lead to less fluid resuscitation volume requirement for a given physiological effect, often cited as a ratio of 3:1 [14]. Recent understanding of the pathophysiological effects of sepsis on the glycocalyx in the endothelial wall suggest HAS might have important protective effects that could translate into clinical benefit; however, this potential benefit is controversial and unsubstantiated in clinical trials [15]. Importantly, glycocalyx injury is exacerbated by rapid fluid expansion and hypervolaemia, both of which may occur during early fluid resuscitation. HAS has a number of additional biological properties that may benefit oxygen delivery and end organ perfusion over and above circulating volume expansion in patients with infection and sepsis. Albumin is a key antioxidant in plasma scavenging oxygen free radicals [17-23] and acts as a transport protein binding inflammatory mediators [24]. Moreover, in animal models albumin improves myocardial function and oxygenation [25]. Laboratory studies suggest it is an essential component of the endothelium and may affect vascular permeability and endothelial dysfunction in sepsis [26-29]. As noted above, laboratory evidence suggests it may reduce damage to the glycocalyx in patients with sepsis [30].

***Relevance and importance for current UK clinical practice now:*** The vast majority of patients with community acquired sepsis are managed in general wards in the NHS. This group is extremely common and has long lengths of hospital stay. The mortality rate for this patient group remains stubbornly high and there is limited scope for evidence based practice to lower it further. One possible beneficial intervention is intravenous fluid resuscitation. There is a paucity of evidence around type, timing and volume of intravenous fluid and this trial directly addresses this area. If HAS was shown to be superior the impact for NHS practice would be substantial, would improve patient experience and relieve suffering and would radically change the current NICE and international guidelines [1,2]. Conversely, if HAS is shown not to be superior, then the non-evidence based current drift of clinicians to extrapolate use of HAS to all sepsis settings could be curtailed, which would ensure patients only receive necessary treatment and also have significant cost savings for UK and international healthcare. The importance of this subject area to clinicians is evident by the clear support for a trial in this area from a recent international survey [6] and a 31/31 respondent agreement to participate rate from our recent survey.

## **2. STUDY OBJECTIVES**

### **2.1 OBJECTIVES**

#### **2.1.1 Primary Objective**

This trial aims to investigate:

- the feasibility of being able to recruit adults with community acquired sepsis and a National Early Warning Score (NEWS or NEWS2) of  $\geq 5$  in the Emergency Department
- the comparative effectiveness, by determining 30-day mortality, of intravenous 5% Human Albumin compared with intravenous balanced crystalloid in the early resuscitation phase of management of adults with community acquired sepsis.

#### **2.1.2 Secondary Objectives**

1. To assess the mortality rate during index hospitalisation, in-hospital and at 90 days;
2. To assess the ability to deliver the trial including the time to first dose, data completeness and participant withdrawal;
3. To quantify the proportion of patients who receive any other fluid apart, from the one being studied, in the first 6 hours after recruitment;
4. To assess the total volume of intravenous fluid in each arm at 6 hours and 24 hours
5. To assess the level of critical care interventions administered;
6. To investigate the length of hospital stay including critical care (HDU/ICU) admission;
7. To investigate the proportion of patients readmitted to hospital in first 90 days after discharge;
8. Delineate the proportion of patients developing any complications including acute kidney injury, pulmonary oedema and allergy including severe allergic reactions;
9. To assess patient quality of life measures using EQ-5D-5L questionnaire;
10. To assess secondary care costs at 30 days.

### **2.2 ENDPOINTS**

#### **2.2.1 Primary Endpoint**

1. Recruitment rate from screening logs
2. 30-day mortality

#### **2.2.2 Secondary Endpoints**

[figure not shown]
1. In-hospital mortality and 90-day mortality;
2. Time to start of IMP;
3. Data completeness;
4. Study withdrawal;
5. Volume of randomised fluid delivered in each arm in the first 6hrs and 24hrs;
6. Proportion of participants needing critical care intervention: Intravenous vasopressors, renal replacement therapy and invasive ventilation;

7. Proportion of patients who receive any other fluid apart from intervention or control in first 6 hrs after recruitment;
8. Proportion of patients admitted to critical care (HDU/ICU); length of stay in critical care (HDU/ICU);
9. Length of hospital stay;
10. Proportion of patients readmitted in first 90 days after discharge;
11. Proportion of patients developing any of: acute kidney injury (Defined by NICE (<https://cks.nice.org.uk/acute-kidney-injury#!scenario>); pulmonary oedema (Radiology diagnosis or requirement for rescue management (new diuretic use); and allergy or anaphylaxis (Requirement for rescue management (antihistamines, adrenaline, intravenous fluids, steroids));
12. Health Related Quality of life (EQ-5D-5L) at 7 and 180 days for the first 50 patients;
13. Secondary care costs at 30 days (calculated from readmissions and length of stay at ward level and in critical care (HDU/ICU).

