## **4.2 INCLUSION CRITERIA**

Adult patients (18 years or older) who present to UK NHS hospitals with community acquired sepsis meeting all of the 5 criteria:

1. Clinically suspected or proven infection resulting in principal reason for acute illness;
2. NEWS/NEWS2 score  $\geq 5$ ;
3. Hospital presentation within last 12hrs;
4. Clinician decision has been made that immediate (within 1 hour of assessment) intravenous fluid resuscitation is needed; and;
5. Ability to obtain informed consent.

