### **6.3 DOSING REGIME**

Participants allocated to the treatment arm will receive intravenous 5% Human Albumin Solution (HAS) administered as the sole intravenous resuscitation fluid during the initial 6-hour resuscitation period. It is anticipated that most participants will receive approximately 10ml/kg in the first 3 hours using 250-500ml rapid infusion (bolus) of HAS for resuscitation based on clinical judgement, using clinical assessment supplemented by technology within the usual scope of practice. After 3 hours, further HAS boluses for resuscitation up to 6 hours post-randomisation will be at clinical discretion and will be documented in the eCRF. Both vital signs and lactate, if measured, prior to treatment starting and at 1,3,5,7 hours (+/-30mins) after randomisation, will be recorded in the eCRF as well as source data worksheets or medical notes.

To avoid contamination, participants in the HAS arm should not receive balanced crystalloid or other fluid as a resuscitation fluid in the first 6 hours post randomisation. If the treating clinician believes resuscitation to euvolaemia has been completed within the 6hour period post randomisation and wishes to commence slow maintenance fluid within this timeframe using balanced crystalloid, this should be at a rate of no more than 125ml/hour. The reason for the fluid should be clearly recorded in the eCRF i.e., maintenance rather than resuscitation. In the subsequent event of further clinical deterioration during the intervention timeframe requiring resuscitation fluid, further boluses of HAS should be administered and documented as further bolus fluid for resuscitation.

Participants allocated to the usual care arm will receive intravenous balanced crystalloid administered as the sole intravenous fluid during the initial 6 hour resuscitation period post randomisation. It is anticipated that most participants will receive approximately 30ml/kg in the first 3 hours using 250-1000ml rapid infusion (bolus) of balanced crystalloid for fluid resuscitation based on clinical judgement, using clinical assessment supplemented by technology within the usual scope of practice. Thereafter, further crystalloid boluses for resuscitation up to 6 hours will be at the discretion of the clinical team and will be documented in the eCRF. Both vital signs and lactate, if measured, prior to treatment starting and at 1,3,5,7 hours (+/-30mins), will be recorded in the eCRF as well as source data or medical notes.

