### **6.7.4 Concomitant Medications**

No concomitant medications will be recorded as part of the eCRF. These will be documented in the medical records and will only be recorded where they are relevant to AE/SAE reporting.

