#### 4.6 Other analyses

The following data will be summarised descriptively, by randomised group and overall:

A	B	C
	Objective	Endpoints to display
1	Assess mortality rate during index hospitalisation, in-hospital and at 90 days	a) In-hospital mortality (index admission) and b) 90-day mortality
2	Assess the ability to deliver the trial including the time to first dose, data completeness and participant withdrawal	Data completeness (%)
3	Assess the total volume of intravenous fluid in each arm at 6 hours and 24 hours	Volume of randomised fluid delivered in each arm a) in the first 6hrs and b) more than 6hrs to 24hrs
4	Assess the level of critical care interventions administered	Proportion of participants needing critical care intervention: a) Intravenous vasopressors, b) renal replacement therapy and c) invasive ventilation
5	Investigate the length of hospital stay including critical care (HDU/ICU) admission	a) Proportion of patients admitted to critical care (HDU/ICU) b) Length of stay in critical care (HDU/ICU) c) Length of hospital stay
6	Investigate the proportion of patients readmitted to hospital in first 90 days after discharge	Proportion of patients readmitted in first 90 days after discharge

A	B	C
7	Delineate the proportion of patients developing any complications including acute kidney injury, pulmonary oedema and allergy including severe allergic reactions	Proportion of patients developing each, or any, of: a) acute kidney injury (as defined by NICE https://cks.nice.org.uk/acute-kidney-injury#!scenario ); b) pulmonary oedema (radiology diagnosis or requirement for rescue management (new diuretic use)); and c) allergy or anaphylaxis (requirement for rescue management (antihistamines, adrenaline, intravenous fluids, steroids))
For the economist		
8	To assess patient quality of life measures using EQ-5D-5L questionnaire	Health Related Quality of life (EQ-5D-5L) for the first 50 patients randomised (see section 4.8) a) at baseline b) at 7 days and c) at 180 days
9	To assess secondary care costs at 30 days	Service use at 30 days: a) number of readmissions, and b) length of stay at ward level and in critical care (HDU/ICU)

In addition, the following exploratory analyses will be considered. If deemed inappropriate based on available data, where feasible, suitable alternatives will be used:

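### Allergy/anaphylaxis and diuretic-only pulmonary oedema are defined by treatments with no stated link to the event, and one of those treatments is given to every participant

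*Protocol*

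**What the plan says.** Protocol 2.2.2, item 11, counts participants who develop acute kidney injury, pulmonary oedema, or allergy/anaphylaxis. Kidney injury is tied to a NICE definition. The other two are defined in brackets:

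- "pulmonary oedema (Radiology diagnosis or requirement for rescue management (new diuretic use"
- "allergy or anaphylaxis (Requirement for rescue management (antihistamines, adrenaline, intravenous fluids, steroids"

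The same wording stands in the Trial Summary and in the Protocol 8.1 outcome list. SAP 4.6 row 7 carries it over as "allergy or anaphylaxis (requirement for rescue management (antihistamines, adrenaline, intravenous fluids, steroids" and reports it as "Proportion of patients developing each, or any, of" the three complications. None of these places gives a clinical sign, a time window, or a statement that the drug or fluid must have been given for the event.

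Other sections bear on this:

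- Inclusion criterion 4 (Protocol 4.2): "Clinician decision has been made that immediate (within 1 hour of assessment) intravenous fluid resuscitation is needed".
- Protocol 6.3 anticipates "approximately 10ml/kg in the first 3 hours using 250-500ml rapid infusion (bolus) of HAS" in one arm and "approximately 30ml/kg in the first 3 hours using 250-1000ml rapid infusion (bolus) of balanced crystalloid" in the other. Protocol 5.5.3 confirms that treating clinicians know the allocation.
- Protocol 6.7.4: "No concomitant medications will be recorded as part of the eCRF". It then allows an exception where a drug is relevant to AE/SAE reporting. Protocol 8.1 nevertheless lists prescriptions and chest x-rays among the data collected.
- Protocol 11.6.2 exempts pulmonary oedema and allergy or anaphylaxis from SAE reporting to the sponsor. Protocol 11.5 puts only serious, sponsor-reportable events on AE logs and SAE forms.
- The opening of Protocol section 11 says that anaphylaxis will be captured through the secondary outcomes and shown to the DMC.

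**The concern.** A treatment can stand in for a diagnosis only if it is seldom given for any other reason, or if the record shows why it was given. For allergy, one of the four listed treatments is the trial intervention itself. For pulmonary oedema, a new diuretic qualifies with no lung finding, in a trial where the arms are expected to receive different fluid volumes and prescribers know the arm.

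Without a written attribution rule, about 15 sites must each supply their own. Background treatment counted as events pulls a real difference towards no difference. If background treatment differs between arms, it can also create a difference that is not there. Because the exemption removes these events from the AE logs, the SAP 4.7 tables and 4.9 listings are unlikely to show them. Item 11 therefore carries most of the structured information on two harms that matter for the definitive trial, including the anaphylaxis data for the DMC.

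**Working it through.** **Reading the text.** The documents state no figure for item 11, so there is nothing to reproduce.

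1. *Allergy.* The qualifying set is antihistamine, adrenaline, intravenous fluid or steroid. Criterion 4 requires a need for intravenous fluid in everyone, and 6.3 gives it in both arms. The fluid element is therefore present for every participant and carries no information. Attribution does not fully rescue it. Under 6.3, further boluses for deterioration within the six hours are documented as resuscitation fluid, so a bolus given for a reaction is hard to tell from one given for sepsis.
2. *Pulmonary oedema.* There are two routes joined by *or*. The radiology route does not depend on treatment. The diuretic route needs no lung finding.
3. *Record of the reason.* 6.7.4 keeps concomitant drugs off the eCRF except for AE/SAE reporting, from which these events are exempt. 8.1 lists prescriptions but not indication. The two sections do not agree, and neither provides for the reason to be recorded.
4. *Other capture.* 11.5 with 11.6.2 leaves exempt events in the medical notes and in item 11. The Protocol 7.1 schedule collects them at discharge. No blinded adjudication is described.

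**Illustration (all rates are assumptions).** Let *t* be the true event rate and *f* the share of participants without the event who receive a listed treatment for another reason. The recorded rate is *t* + (1 − *t*)*f*. With 300 randomised 1:1, there are 150 per arm.

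*Equal background, assumed true allergy 3% (HAS) and 1% (crystalloid):*

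| *f* | HAS | Crystalloid | Ratio |
|---|---|---|---|
| 0 | 3.0% | 1.0% | 3.0 |
| 5% | 0.03 + 0.97×0.05 = 7.85% | 0.01 + 0.99×0.05 = 5.95% | 1.32 |
| 10% | 0.03 + 0.97×0.10 = 12.7% | 0.01 + 0.99×0.10 = 10.9% | 1.17 |
| 20% | 0.03 + 0.97×0.20 = 22.4% | 0.01 + 0.99×0.20 = 20.8% | 1.08 |
| 100% | 100% | 100% | 1 |

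At *f* = 10%, 0.03/0.127 = 24% of counted HAS events and 0.01/0.109 = 9% of counted crystalloid events are true. The last row is what counting any intravenous fluid would give.

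*Unequal background, no true difference, assumed pulmonary oedema 5% in both arms:*

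- *f* = 5% against 10%: 0.05 + 0.95×0.05 = 9.75% against 0.05 + 0.95×0.10 = 14.5%, a gap of 4.75 points. It is nominally significant (two-sided 5%) about 24% of the time.
- *f* = 10% against 20%: 14.5% against 0.05 + 0.95×0.20 = 24%, a gap of 9.5 points. It is nominally significant about 55% of the time.

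Swapping the two values of *f* reverses the sign. The gap is essentially the assumed difference in *f*, so this shows the mechanism and is not an estimate.

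**The case against.** The strongest reply is that the brackets are being read too literally. Item 11 counts patients who develop a complication, and rescue management most naturally means treatment for that complication. Objective 8 speaks of complications, the 7.1 schedule has an allergy/anaphylaxis entry at discharge, and section 11 refers to anaphylaxis events. Resuscitation fluid needed at entry is not something developed later. This stands. A reader might infer that all 300 participants would be coded as allergic, or that the endpoint cannot isolate harm. The documents do not support either, because both need a reading that sites are unlikely to adopt.

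It is also fair that pulmonary oedema has a radiology route and that row 7 shows each complication separately, so a loose allergy count cannot hide kidney injury or oedema. The combined *any* line does inherit the weakest component. Drugs remain in the medical notes, and on-site monitoring is foreseen (Protocol 12.6). It therefore goes too far to say that the indication could never be checked.

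A reader might further infer that diuretic-only cases bias the comparison in favour of HAS by several points. Nothing in the documents gives diuretic rates. More offloading after a larger volume could be a genuine effect of the allocated fluid rather than bias. That steroids, adrenaline, antihistamines or diuretics are used for other reasons in sepsis is clinical inference, not something the documents state.

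What the reply does not remove is that the attribution rule is nowhere written, that the SAP repeats the wording without clarifying it, and that one listed qualifier cannot discriminate in this trial. Even if diuretic use reflects a real volume effect, it should not be labelled pulmonary oedema without documentation of pulmonary oedema.

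**Conclusion.** The point holds as a defect of definition. Allergy/anaphylaxis is identified solely by treatments, one of them universal. Pulmonary oedema may be identified by a new diuretic alone. Neither is tied in writing to the event. This is more than missing detail, because a stated qualifier carries no information and a stated proxy can relabel non-pulmonary diuretic use. The exemption from sponsor reporting raises its importance, since item 11 becomes the main structured record of these events.

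The size and direction of any distortion cannot be derived from the documents. The illustrative figures rest entirely on assumed rates and show only that equal background treatment dilutes a true difference and unequal background can produce a false one either way. These are secondary outcomes in a feasibility trial with informal, descriptive testing (Protocol 10.2, SAP 3), and neither primary outcome is touched. The change should be made, but it is not critical.

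**What to change.** In Protocol 2.2.2 item 11, the Trial Summary, 8.1 and SAP 4.6 row 7:

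- Count allergy/anaphylaxis only when a clinician-documented reaction after randomisation was the recorded reason for treatment. Do not count intravenous fluid alone as a qualifying treatment.
- Report pulmonary oedema on two lines: radiology-diagnosed, and diuretic-only. The second requires documented pulmonary oedema as the indication.
- Reconcile 6.7.4 with 8.1 so that the qualifying drug and its indication are recorded.

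The cost is wording in both documents and an indication field on the discharge eCRF page. The SAP abstract describes recruitment in the past tense, so the eCRF may be closed. In that case, make the change in SAP row 7 from the chest x-ray and prescription data that 8.1 lists. Label any diuretic-only case whose indication is not recorded as unattributed.

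There are two downsides. A few undocumented reactions, or reactions treated with fluid alone, would be missed. Attribution would still be made by clinicians who know the arm. Adjudication of these few events from notes with the allocation masked would reduce the second problem at some extra cost.
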